### 9.4. Vital Signs

Values at each scheduled timepoint, change, and percentage change from baseline for vital signs, including systolic blood pressure, diastolic blood pressure, pulse, temperature, and respiratory rate will be summarized descriptively.

Normal ranges for vital sign values are defined in [Table 4](#). The abnormal values for subjects exhibiting vital sign abnormalities will be listed along with their assigned dose level. Alert vital signs are defined as an absolute value outside the defined normal range and percentage change greater than 25%. The abnormal values for subjects exhibiting alert vital sign abnormalities will be listed.

**Table 4: Normal Ranges for Vital Sign Values**

Parameter	High Threshold	Low Threshold
Systolic blood pressure	> 155 mmHg	< 85 mmHg
Diastolic blood pressure	> 100 mmHg	< 40 mmHg
Pulse	> 100 bpm	< 45 bpm
Temperature	> 38°C	< 35.5°C
Respiratory rate	> 24 breaths/min	< 8 breaths/min

### 9.5. Electrocardiograms

Twelve-lead ECGs including PR, RR, QT, QRS, QTcB, and QTcF intervals will be obtained for each subject during the study. Values at each scheduled timepoint, change, and percentage change from baseline will be summarized for each ECG parameter. Baseline will be determined as the average of all nonmissing values before the first administration of INCB059872 (Parts 1 and 2), INCB059872 and ATRA (TGs C and C1), INCB059872 and azacitidine (TGs D and D1), or INCB059872 and nivolumab (TGs E and E1).

Normal ranges for ECG values are defined in [Table 5](#). Electrocardiogram values will also be considered abnormal if the absolute percentage change from baseline is more than 25% (30% for QRS interval). Subjects exhibiting ECG abnormalities will be listed with study visit and assigned dose level. Abnormal values for subjects with alert ECG values, defined as both the absolute value and the percentage change from baseline being outside normal ranges, will be identified and listed. Outliers of QT, QTcB, and QTcF values, defined as absolute values > 450 ms, > 500 ms, or change from baseline > 30 ms, will be summarized.

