### 3.2. Subject Exclusion Criteria

A subject who meets any of the following criteria will be excluded from the study:

1. Receipt of anticancer medications, anticancer therapies, or investigational drugs within the following interval before the first administration of study drug (requirement may be waived with medical monitor approval):
  - a. < 5 half-lives or 14 days, whichever is longer, for any investigational agent
  - b. < 5 half-lives for all other anticancer medications
  - c. < 6 weeks for mitomycin-C or nitrosoureas
2. Any unresolved toxicity  $\geq$  Grade 2 from previous anticancer therapy except for stable chronic toxicities ( $\leq$  Grade 2) not expected to resolve.
3. All treatment groups: prior receipt of an LSD1 inhibitor therapy. Parts 3 and 4 TG E/E1: prior receipt of anti-PD-1, anti-PD-L1, or anti-PD-L2 antibody.
4. Any of the following laboratory results at screening without transfusions and hematopoietic growth factor support in solid tumors (no lower limits in AML and MDS, or in MF with medical monitor approval):

Laboratory Parameter	Value
Absolute neutrophil count ( $\times 10^9/L$ )	< 1.5
Hemoglobin (g/dL)	< 9.0
Platelet count ( $\times 10^9/L$ )	< 100

5. Laboratory and medical history parameters outside Protocol-defined range unless associated with primary malignancy or metastatic disease and with medical monitor approval:
  - a. Total bilirubin  $> 1.5 \times$  institutional upper limit of normal (ULN) if no liver metastases or  $> 3 \times$  ULN in the presence of liver metastases or presence of documented Gilbert syndrome (unconjugated hyperbilirubinemia).
  - b. Aspartate aminotransferase (AST) or alanine aminotransferase (ALT)  $> 2.0 \times$  institutional ULN.
  - c. Creatinine clearance  $< 60$  mL/min based on the institutional formula.
6. History or evidence of bleeding disorder requiring treatment.
7. History or presence of an abnormal ECG that in the investigator's opinion is clinically meaningful. A screening QTc interval  $> 470$  milliseconds, as corrected by Fridericia, is excluded. For subjects with an intraventricular conduction delay (QRS interval 120 milliseconds), the JTc interval may be used in place of the QTc with sponsor approval. Subjects with left bundle branch block are excluded.

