#### 9.4.3.3. Vital Signs

Descriptive statistics and mean change from baseline will be determined for vital signs (blood pressure, pulse, respiratory rate, and body temperature) at each assessment time. Vital sign results will be reviewed for clinically notable abnormalities (see [Table 12](#)), and subjects exhibiting clinically notable vital sign abnormalities will be listed. A value will be considered an "alert" value if it is outside the established range and shows a > 25% change from baseline.

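### The 25% relative-change condition leaves the alert listings unworkable for body temperature and too coarse for QTc, and the > 450 ms outlier count ignores the baseline value

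*SAP*

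**What the plan says.** **Vital signs.** SAP 9.4 states: "Alert vital signs are defined as an absolute value outside the defined normal range and percentage change greater than 25" per cent. Protocol 9.4.3.3 agrees, calling a value an alert if it is "outside the established range and shows a > 25% change from baseline". The temperature limits are above 38 °C and below 35.5 °C (SAP Table 4; Protocol Table 12).

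**ECG.** SAP 9.5 uses a percentage test in two ways. First, a value also counts as abnormal if the "absolute percentage change from baseline is more than 25% (30% for QRS interval"). Second, an alert is "defined as both the absolute value and the percentage change from baseline being outside normal ranges". SAP Table 5 puts the high limit for QTcF and QTcB at 470 ms. Protocol 9.4.3.4 has neither a percentage test nor an alert category for ECGs, so both are SAP additions.

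**QT outliers.** The same SAP section summarizes QT, QTcB and QTcF outliers, "defined as absolute values > 450 ms, > 500 ms, or change from baseline > 30 ms, will be summarized". It sets no condition on the baseline value. For ECGs, "Baseline will be determined as the average of all nonmissing values before the first administration of INCB059872" (and, in Parts 3 and 4, of the partner drug).

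**Entry.** Under exclusion criterion 7 in Protocol 3.2, a screening QTc above 470 "milliseconds, as corrected by Fridericia, is excluded". Values up to 470 ms are therefore admitted. Protocol Appendix K dates this limit to Amendment 6. SAP 2.1 says the SAP was written on Amendment 5 and stays in force for later amendments.

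**The concern.** One relative-change limit is applied to quantities with very different scales. A 25% change is a reachable condition for blood pressure or pulse. It is not reachable for body temperature, whose Celsius value barely moves in relative terms even in high fever. For QTc it demands a rise several times larger than the change the SAP itself treats as notable.

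Vital signs and ECGs are part of the primary safety endpoint in all four parts (Protocol 2.2.1; SAP 2.3.1). An alert listing is read as the short list of values that matter most. If its temperature section is empty by construction, a reader may take the silence as reassurance. Fever is relevant here: febrile neutropenia is a dose-limiting toxicity in solid tumors (Protocol Table 4) and was reported in 5 of 17 TG A subjects (Protocol Table 2).

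The > 450 ms row raises a separate problem. With no baseline condition, it mixes subjects who were already above the cut-off before dosing with those who crossed it on treatment.

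**Working it through.** The plan states no figure for this point, so there is nothing to reproduce. The rule can be applied directly.

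**Rule.** With baseline B and on-study value V, a high alert needs V > upper limit and V > 1.25 × B. A low alert needs V < lower limit and V < 0.75 × B.

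**Temperature (limits 38 and 35.5 °C).**
- B = 36.8: high alert above 36.8 × 1.25 = 46.0 °C; low alert below 36.8 × 0.75 = 27.6 °C.
- B = 35.5: above 44.4 °C. B = 38.0: above 47.5 °C.
- In reverse, a reading of 38.1 °C is an alert only if baseline was below 38.1 / 1.25 = 30.5 °C, and a reading of 42 °C only if it was below 33.6 °C.

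By contrast, a systolic pressure at the 155 mmHg limit needs a baseline below 155 / 1.25 = 124 mmHg, and a pulse at 100 bpm needs one below 80 bpm. Both are ordinary values, so the condition can operate there.

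**QTcF (limit 470 ms).** V > 1.25 × B means B < V / 1.25, so the rise V − B exceeds V / 5. Two results follow without any assumption about the data:
- An alert needs V > 470, so the rise must exceed 470 / 5 = 94 ms.
- If V > 500, the rise must exceed 500 / 5 = 100 ms. A value above 500 ms reached by a rise of 100 ms or less is never an alert.

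| Baseline QTcF (ms) | Alert only above (ms) | Rise must exceed (ms) |
|---|---|---|
| 376 | 470 | 94 |
| 400 | 500 | 100 |
| 420 | 525 | 105 |
| 450 | 562.5 | 112.5 |
| 470 | 587.5 | 117.5 |

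Example: 420 to 520 ms is a change of 100 / 420 = 23.8%. It is not an alert, although the rise is more than three times the SAP's 30 ms outlier change.

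**The > 450 ms count.** A subject at 460 ms before and after dosing is within the Table 5 range and has zero change, yet is counted as above 450 ms. The documents do not give the distribution of baseline QTcF, so the number of such subjects is unknown. For illustration only, assume normal baselines with mean m = 400 to 430 ms and SD s = 15 to 25 ms, truncated at 470. The share between 450 and 470 is [Φ((470 − m)/s) − Φ((450 − m)/s)] / Φ((470 − m)/s). It runs from 0.04% (m = 400, s = 15) to 17% (m = 430, s = 25).

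**The case against.** The strongest reply is that nothing is lost, and that is correct. An alert is a subset of the abnormal values. Any temperature outside the Table 4 limits goes into Listing 2.9.2, and any QTcF above 470 ms into Listing 2.10.2. Table 3.5.7 counts values above 500 ms and changes above 30 ms. The 420 to 520 ms example appears in all the relevant ECG displays except Listing 2.10.3. For the abnormal ECG listing, the percentage test adds a route in and so widens capture. A reader might infer that fever and QTc prolongation vanish from the report; the documents do not support that.

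Three other stronger readings also fail:
- **The alert flag steers treatment or dose decisions.** No dose-limiting toxicity, dose-modification or discontinuation rule in the Protocol refers to it. ECGs are read by the investigator and by a central vendor.
- **Most QTcF values above 500 ms would miss the alert listing.** That depends on baseline and change distributions the documents do not give. A simulation over assumed normal distributions (baseline mean 390 to 430 ms, SD 15 to 25, truncated at 470; change mean 0 to 20 ms, SD 15 to 40) put the share of such values that are alerts anywhere from 0% to 70%. Only the assumption-free statements above should be used.
- **The > 450 ms row attributes entry values to the drug.** The SAP only summarizes the count, in a descriptive analysis. The table shells are in a separate document, so it cannot be seen whether Table 3.5.7 shows baseline status.

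It can also be said that dropping subjects with high baselines from the outlier count would hide a rise from 455 to 470 ms, which neither exceeds 470 ms nor changes by more than 30 ms. That stands, and the fix below allows for it.

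**Conclusion.** The point holds for the alert listings and for the > 450 ms row. The temperature part of Listing 2.9.3 will in practice be empty, because no plausible pair of readings meets the rule. Listing 2.10.3 cannot contain a high QTcF alert with a rise of 94 ms or less, nor a value above 500 ms with a rise of 100 ms or less. These statements rest only on the SAP's limits and on reading 25% as the percentage range meant in the ECG alert sentence; Table 5 itself gives no percentage range.

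The > 450 ms count includes subjects already above 450 ms before dosing, because the Protocol from Amendment 6 onward admits screening QTcF up to 470 ms and the SAP sets no baseline condition. How many subjects this concerns cannot be determined from the documents.

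The effect is limited to how safety values are displayed and read. It should be corrected because vital signs and ECGs belong to the primary endpoint and the limits needed are already in the SAP.

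**What to change.** 1. **SAP 9.4 and Protocol 9.4.3.3:** drop the percentage condition for temperature and define the alert by the range limits alone (SAP Table 4, identical to Protocol Table 12). Temperature entries in Listing 2.9.3 will then match those in Listing 2.9.2; this duplication is acceptable.
2. **SAP 9.5:** for high QTcF and QTcB, replace the percentage condition with either a value above the Table 5 limit together with an increase of more than 30 ms, or any value above 500 ms. The 420 to 520 ms case then becomes an alert.
3. **Table 3.5.7:** show the > 450 and > 500 ms categories by baseline category, as a shift display. Alternatively, keep the all-subject count and add a new-onset count among subjects at or below the cut-off at baseline. Either way, rises from a high baseline such as 455 to 470 ms stay visible.

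The cost is revised wording in two SAP sections and one Protocol section, minor recoding of the derivations, and longer alert listings. No new data are needed.

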**Table 5: Normal Ranges for Electrocardiogram Values**

Parameter	High Threshold	Low Threshold
PR	> 220 ms	< 75 ms
RR	> 1330 ms	< 600 ms
QT	> 500 ms	< 300 ms
QRS	> 120 ms	< 50 ms
QTcB, QTcF	> 470 ms	< 295 ms

QTcF = Fridericia's correction; QTcB = Bazett's correction.

## **10. INTERIM ANALYSES**

### **10.1. Overview of Interim Analyses**

In Part 4, a stopping rule for futility is planned for each combination dose expansion treatment group when 15 subjects have been treated and evaluated for response or have permanently discontinued study treatment because of disease progression, withdrawal of consent, or death. Combination TG C1 will be terminated for futility if  $\leq 1$  of the 15 subjects responded (ie, CR or CRi based on altering the natural history of the disease) based on assessments provided by the investigator. Combination TG D1 will be terminated for futility if  $\leq 2$  of the 15 subjects responded (ie, CR or CRi based on altering the natural history of the disease) based on assessments provided by the investigator. Combination TG E1 will be terminated for futility if  $\leq 1$  of the 15 subjects responded (ie, CR or PR) based on assessments provided by the investigator. No formal TFLs were planned for interim analyses.

An iDSMB will review safety data at regular intervals throughout the study. Details regarding membership, roles, and responsibilities of the committee are specified in the iDSMB charter. The process by which the iDSMB will make recommendations and decisions is documented in the iDSMB charter.

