**Statistical Methods:**

Sample size consideration: Parts 1 and 3 of the study will use a 3 + 3 dose-escalation design, and the sample size will depend on the frequency of DLTs and the number of dose-escalation cohorts before reaching the MTD. For Part 2, up to approximately 15 subjects will be enrolled for each expansion cohort. The evaluation of 15 subjects will provide a  $\geq 90\%$  chance of observing at least 1 toxicity with a true event rate of  $\geq 15\%$ . For Part 4, for each of the combination cohorts (TG C1, TG D1, and TG E1) up to approximately 30 subjects will be enrolled. The evaluation of 30 subjects will provide approximately 90% chance of observing at least 1 toxicity with a true event rate of  $\geq 7\%$ .

All statistical analyses are exploratory in nature; descriptive statistics (eg, mean, standard deviation, range) will be derived where appropriate. The clinical safety data (vital signs, ECGs, laboratory tests, and AEs) will be descriptively summarized.

Pharmacokinetic [REDACTED] data will be analyzed. For subjects with solid tumor, AML, and MDS, the proportion of subjects who meet the response criteria as appropriate for the tumor type will be [REDACTED] summarized with descriptive statistics.

[REDACTED] For MF subjects, changes and percentage changes of spleen volume from baseline to Week 12 [REDACTED] will be summarized descriptively.

In Part 4, a stopping rule for futility is planned for each combination dose expansion treatment group. The futility analyses for combination TGs will be conducted when 15 subjects for each disease type have been treated and evaluated for response or have permanently discontinued study treatment because of disease progression, withdrawal of consent, or death. The futility analyses for TG D1 will be conducted when the first 15 subjects with AML or when the first 15 subjects with MDS have been treated and evaluated. Combination TG C1 will be terminated for futility if  $\leq 1$  of the 15 subjects responded (ie, CR, CRI, morphologic leukemia-free state [MLFS]) based on assessments provided by investigator.

Combination TG D1 will terminate enrollment for subjects with AML if  $\leq 2$  of the first 15 AML subjects respond (ie, CR, CRI, or MLFS), or will terminate enrollment for subjects with MDS if  $\leq 2$  of the first 15 MDS subjects responded (ie, CR or Marrow CR), based on assessments provided by investigator.

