#### **9.6. Interim Analysis**

In Part 4, a stopping rule for futility is planned for each combination dose expansion treatment group. The futility analyses for combination TGs will be conducted when 15 subjects for each disease type have been treated and evaluated for response or have permanently discontinued study treatment because of disease progression, withdrawal of consent, or death. The futility

analyses for TG D1 will be conducted when the first 15 subjects with AML or when the first 15 subjects with MDS have been treated. Combination TG C1 will be terminated for futility if  $\leq 1$  of the 15 subjects responded (ie, CR, CRi, MLFS) based on assessments provided by investigator. Combination TG D1 will terminate enrollment for subjects with AML if  $\leq 2$  of the first 15 AML subjects responded (ie, CR, CRi, MLFS) or will terminate enrollment for subjects with MDS if  $\leq 2$  of the first 15 MDS subjects responded (ie, CR or marrow CR), based on assessments provided by investigator. Combination TG E1 will be terminated for futility if  $\leq 1$  of the 15 subjects responded (ie, CR or PR) based on assessments provided by investigator.

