## **2. STUDY INFORMATION, OBJECTIVES, AND ENDPOINTS**

### **2.1. Protocol and Case Report Form Version**

This SAP is based on INCB 59872-101 Protocol Amendment 5 dated 30 JUL 2018 and CRFs approved 23 APR 2018. Unless superseded by an amendment, this SAP will be effective for all subsequent Protocol amendments and CRF versions.

[figure not shown]

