In Part 4, a stopping rule for futility is planned for each combination dose expansion treatment group when 15 subjects have been treated and evaluated for response or have permanently discontinued study treatment because of disease progression, withdrawal of consent, or death. Combination TG C1 will be terminated for futility if  $\leq 1$  of the 15 subjects responded (ie, CR or CRi) based on assessments provided by investigator. Combination TG D1 will be terminated for futility if  $\leq 2$  of the 15 subjects responded (ie, CR or CRi) based on assessments provided by investigator. Combination TG E1 will be terminated for futility if  $\leq 1$  of the 15 subjects responded (ie, CR or PR) based on assessments provided by investigator.

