### **10.2. Derivations and Calculations for Interim Analyses**

For each combination expansion group, the futility analysis will be conducted for exactly 15 subjects with the stopping boundary as stated in Section 10.1. There is no efficacy interim analysis planned for the study.

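### The SAP's futility rule for TG C1 and TG D1 predates Amendment 6 and contradicts current protocol 9.6 on who counts as a responder and on how many TG D1 decisions are made

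*SAP*

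**What the plan says.** **SAP.** Section 10.1 terminates TG C1 if 1 or fewer, and TG D1 if 2 or fewer, "of the 15 subjects responded (ie, CR or CRi based on altering the natural history of the disease"). Section 3 gives the same rule: "of the 15 subjects responded (ie, CR or CRi) based on assessments provided by investigator". Section 10.2 adds that, for each combination expansion group, "the futility analysis will be conducted for exactly 15 subjects with the stopping boundary as stated in Section 10.1". Section 3 describes TG D and TG D1 as AML only.

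**Protocol.** Section 9.6 stops TG C1 if 1 or fewer "of the 15 subjects responded (ie, CR, CRi, MLFS) based on assessments provided by investigator". In TG D1 it closes AML enrollment at 2 or fewer responders among the first 15 AML subjects, again counting CR, CRi or MLFS. It closes MDS enrollment separately, at 2 or fewer "of the first 15 MDS subjects responded (ie, CR or marrow CR), based on assessments provided by investigator". The synopsis (Statistical Methods) agrees: AML enrollment stops at 2 or fewer "of the first 15 AML subjects respond (ie, CR, CRI, or MLFS), or will terminate enrollment for subjects with MDS if" the MDS condition is met.

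**Version control.** SAP 2.1 states: "This SAP is based on INCB 59872-101 Protocol Amendment 5 dated 30 JUL 2018 and CRFs approved 23 APR 2018". It continues: "Unless superseded by an amendment, this SAP will be effective for all subsequent Protocol amendments and CRF versions". SAP Table 6 lists only the original version of 01 OCT 2018, and SAP 11.1 records no change to protocol-defined analyses. The protocol's change log places the addition of both MLFS and the TG D MDS subjects in Amendment 6 (2019), after the SAP was written.

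**The concern.** This rule decides whether a cohort closes, and two documents in force state it differently in three respects.

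1. **Responder definition for AML.** A subject whose best result is MLFS counts under the protocol and not under the SAP. The Amendment 6 rationale was to capture responses without platelet recovery, which it attributes to on-target drug activity. The SAP leaves out the responders the sponsor chose to include.
2. **Unit of decision in TG D1.** The protocol decides per disease. The SAP makes one decision for the whole group.
3. **Responder definition for MDS.** The SAP has none. SAP 7.3.3.1 lists the MDS response categories and CRi is not among them, so the SAP's rule applied to an MDS subject reduces to CR alone and marrow CR is lost.

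For AML subjects the discrepancy runs one way: the SAP rule stops at least as often as the protocol rule.

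**Working it through.** **Text comparison**

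| Item | SAP 3, 10.1, 10.2 | Protocol 9.6, synopsis |
|---|---|---|
| TG C1 | at most 1/15; CR, CRi | at most 1/15; CR, CRi, MLFS |
| TG D1, AML | at most 2/15; CR, CRi | at most 2/15; CR, CRi, MLFS |
| TG D1, MDS | not addressed | at most 2/15; CR, marrow CR |
| TG D1 decisions | one, on 15 subjects | one per disease, 15 subjects each |
| TG E1 | at most 1/15; CR, PR | same |

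The cut-offs agree. The conflict is confined to TG C1 and TG D1.

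**Inputs for the size**

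- n = 15 and the cut-offs: both documents.
- CR/CRi of 27.8% for azacitidine alone in newly diagnosed AML: protocol 1.3.2. It is used as an illustration, not as a design rate.
- TG C1 CR/CRi of 5% to 20%: assumed.
- MLFS-only share m, the extra percentage points of subjects reaching MLFS but not CR/CRi: assumed at 5, 10 and 15. At m = 0 the rules agree.

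Neither document states a null rate, a target rate or an error rate for the futility rule, so there is no planned figure to reproduce.

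**Formula.** With p the probability that a subject counts as a responder, P(stop) = P(X ≤ r), X ~ Binomial(15, p), where r = 1 for TG C1 and r = 2 for TG D1. The SAP uses p = CR/CRi; the protocol uses p = CR/CRi + m. Every SAP responder is also a protocol responder, so a protocol stop implies a SAP stop in the same subjects. Hence P(SAP stops, protocol continues) is the difference of the two stopping probabilities.

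**Worked case, TG C1 at CR/CRi 10%, m = 5 points**

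- SAP: 0.90^15 + 15 × 0.10 × 0.90^14 = 0.2059 + 0.3432 = 0.549.
- Protocol: 0.85^15 + 15 × 0.15 × 0.85^14 = 0.0874 + 0.2312 = 0.319.
- Opposite decisions: 0.230.

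**P(stop) across the grid**

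| Group, CR/CRi | SAP | Protocol, m = 5 | m = 10 | m = 15 |
|---|---|---|---|---|
| C1, 5% | 82.9% | 54.9% | 31.9% | 16.7% |
| C1, 10% | 54.9% | 31.9% | 16.7% | 8.0% |
| C1, 15% | 31.9% | 16.7% | 8.0% | 3.5% |
| C1, 20% | 16.7% | 8.0% | 3.5% | 1.4% |
| D1 AML, 27.8% | 16.9% | 8.6% | 3.9% | 1.6% |

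Opposite decisions, taken as differences of unrounded values:

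- TG C1 at 10%: 23.0%, 38.2%, 46.9%.
- TG D1 AML at 27.8%: 8.3%, 12.9%, 15.2%.

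**Small MLFS shares.** For TG C1 at 10%, m = 1 gives 0.549 − 0.497 = 5.2% and m = 3 gives 0.549 − 0.401 = 14.8%.

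**Mixed TG D1 cohort.** No error rate is claimed. TG D1 plans about 30 subjects, so both 15-subject looks are reached only at an exact 15/15 split, and the documents give neither the disease mix nor an MDS rate.

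**The case against.** The strongest reply is that this is version lag, not two competing rules. The SAP describes itself as detailing analyses outlined in the protocol and plans no formal interim outputs. Its clause on supersession can be read as letting a later protocol amendment prevail, in which case protocol 9.6 governs and the SAP is merely out of date. That reading is available, but SAP 2.1 does not say whose amendment supersedes. Under either reading the SAP prints a contrary rule and contains none that matches protocol 9.6.

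The second reply is that the percentages depend on assumed MLFS shares. Protocol Appendix D already classes a subject who misses CR only through residual neutropenia or thrombocytopenia as CRi, so the MLFS-only share could be under 5 points. This is fair: the percentages are illustrations. Even so, 1 to 3 points give about 5% to 15% opposite decisions in TG C1 at 10%, and the textual conflict needs no rate.

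Third, the SAP calls TG D1 AML only and so never claims to apply CR/CRi to MDS. That is true, but the SAP then has no rule for subjects the protocol enrolls. The reply also notes that protocol 2.2.2 names CRi in a joint AML/MDS endpoint although Appendix F has no such category. That is correct; its qualifier that the criteria apply as applicable, together with SAP 7.3.3.2.1 (CR only), resolves it in practice.

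Finally, the study is exploratory with safety as its primary endpoint. That limits the severity, but the rule still closes enrollment.

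**Conclusion.** The concern holds with high confidence as a conflict between current texts. The SAP's stopping rule for TG C1 and TG D1 is wrong as written on the AML responder definition and on the unit of decision in TG D1, and it has no MDS rule. For AML subjects the SAP can only stop more often. How much more depends on an MLFS rate that the documents do not give, so the tabulated probabilities show a plausible range and are not estimates. The boundaries, the TG E1 rule, the final AML ORR (CR or CRi in both documents) and the primary safety analysis are not affected. It should be fixed before any Part 4 futility look.

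**What to change.** Issue one SAP amendment that:

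- replaces the responder definitions in sections 3 and 10.1 with those of protocol 9.6: CR, CRi or MLFS for TG C1 and TG D1 AML; CR or marrow CR for TG D1 MDS;
- rewrites section 10.2 so that TG D1 has separate looks at the first 15 AML and the first 15 MDS subjects, each closing only that disease, and says what happens if one disease does not reach 15;
- corrects the AML-only description of TG D and TG D1 in section 3;
- updates the protocol version in section 2.1 and records the change in section 11.

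As minor alignment, add the Parts 3 and 4 MDS endpoint to SAP 2.3.2, using the MDS responder definition already in 7.3.3.2.1 so that an undefined CRi category is not carried over. State in 5.2 that Group D best overall response and ORR are reported separately for AML and MDS. The Appendix A split is a display matter that can follow.

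No extra data or subjects are needed: SAP 7.3.2.1 and 7.3.3.1 already record MLFS and marrow CR at each assessment. The cost of splitting Group D is wider intervals; for example, the exact 95% interval is 7.7% to 38.6% for 6/30 and 4.3% to 48.1% for 3/15.
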